7.5 Withdrawal Visit

An early termination visit will be performed if a participant is suspended before the completion of the study, prior to withdrawal of consent and with the participant's permission. This could happen during a scheduled or unscheduled visit. The investigator, study coordinator or research staff will discuss with the participant to contact the research team in case AE arise after the withdrawal visit. The assessment and procedures of Visit 4 will be conducted at this visit.

7.6 Unscheduled Visit

These visits may occur at the discretion of the investigator. Reasons may include but not limited: The need for withdrawal of the study; the participant is not able to attend a scheduled visit on a specific date; inability to collect the blood sample at the scheduled visit and in case of an Adverse Effect.

8 STUDY PROCEDURES /EVALUATIONS

8.1 Study Procedures/Evaluations

- **Medical History**

The medical history will be taking by trained personnel during the interview and will be entered into the eCRF and will be updated each visit. As a part of the medical history, the study staff will administer a symptom inventory to assess/screen for possible AEs anticipated with the use of Erenumab throughout the study (V1-V5). Staff will record and evaluate new or worsened symptoms as possible AEs

- **Medications and other therapies**

Pharmacological therapies such as prescription and OTC medications and non-pharmacological therapies used in the last 30 days prior Visit 0 will be recorded by trained personnel in the eCRF and will be updated in each visit.

- **Vital Signs and weight collection**

After the medical history is taken, trained personnel will take the blood pressure and collect height and weight. Weight collection and blood pressure reading will be performed in each visit.

- **Pregnancy Test**

Erenumab is not recommended to use during pregnancy, therefore female participants of childbearing potential will be screened for pregnancy with a urine test (instant type) that will be performed at every study visit. The results will be read by the study staff. The urine will be discarded after the test.

- **Blood Collection**

A blood sample will be collected at Visits 0 and 4 by staff trained in phlebotomy. Blood samples will be evaluated then for the presence of [REDACTED] cytokines by Luminex assay.

- **TMD Examination**

The TMD examination will be performed according the Diagnostic Criteria for Temporomandibular Disorders (DC-TMD) [7] by trained and calibrated staff. The examination consists of bilateral digital palpation of masticatory muscles (masseter and temporalis) as well as the palpation of the temporomandibular joint (TMJ) and the manipulation of the jaw to assess if these elicit pain in these structures.

The participant must meet 2 of the criteria for TMD listed in the inclusion criteria: 1) reported pain or ache in the face, jaw/mandible, pre-auricular area, inside the ear or temple that is modified by jaw function. 2) finding(s) of TMD myalgia according to the classification DC-TMD criteria.

- **Pressure Pain Thresholds**

The Pressure Pain Threshold (PPT) will be defined as the amount of pressure at which the participant first perceives pressure to be painful. The PPT measurements will be performed by trained staff using a pressure algometer (Wagner, Greenwich, CT). Calibrated pressured will applied bilaterally over the masseter, temporalis, upper trapezius, the TMJs, and the lateral epicondyles. One pre-trial assessment will be performed at each anatomic structure followed by additional assessments until 2 measures differing by less than 0.2 kg are obtained, or 5 assessments are administered. In either case, the mean of the 2 closest values will be recorded as the threshold estimate. Pressure stimuli will be delivered at an approximate rate of 1 kg/s. The cutoff pressure for all sites will be 5 kg. The values from the right and left sides will be averaged to obtain a single PPT value per anatomical site [34, 35].

- **Daily Symptom Diary**

Participants will be asked to complete the Daily Symptom Diary at the end of each day during the baseline phase and during the study (visits 1-5).

Participants should have at least 80 % compliance with the DSD.

The diary collects the participant's pain intensity (reported on a 0-100 numeric rating scale) and duration (reported on a 0-100 percentage scale), pain days and use of pain medication. Participants are required to complete a Daily Symptom Diary electronically or on paper and a new form will be used for each month of the study. These forms may be returned in person at study visits.

Outcome Measure Questionnaires

Listed in the Schedule of Events (Appendix A). Questionnaire forms on paper will be provided to the participants if an electronic form is not feasible.

Some questionnaires are self-administered, and others will be administered by trained study staff.

- Jaw Functional Limitation Scale. This is a 20-item instrument that measures limitations across 3 domains related to TMJ biomechanics: masticatory function (6 items), vertical jaw mobility/jaw opening (4 items), and verbal and emotional expression (8 items). Two items are not scored as part of these 3 subscales. A degree of limitation is rated on a 0-10 scale from 0 ("no limitation") to 10 ("severe limitation") [36, 37].
- Oral Behaviors Checklist (OBC). Evaluates parafunctional behaviors and generates a single scale representing the frequency of 21 activities such as clenching, chewing gum, and holding objects between teeth, yawn [38, 39].
- Graded Chronic Pain Scale (GCPS). The GCPS includes 7 items and assesses 2 dimensions of pain: pain intensity and pain-related disability [40].

- Patient Global Impression of Change (PGIC). This instrument measures change in participant's overall status on a scale ranging from 1 (very much improved) to 7 (very much worse). The PGIC is based on the Clinical Global Impression of Change, which is a validated scale [41, 42].
- Hospital Anxiety and Depression Scale. Evaluates anxiety and depression with a 14-item instrument [43].

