3.2.2 Secondary

Efficacy will be investigated further using secondary outcomes:

TMD pain days: Percentage of participants with at least a 50% reduction from baseline in monthly TMD pain days. Time Frame: Baseline phase, the 12 weeks of management and until Visit 4.

Definition of TMD pain day: A TMD pain day was any calendar day in which the participant experienced pain, stiffness, soreness, tenderness, in the jaw or temple area or either side being brief or continuous; and/or pain with TMJ biomechanics (chewing, mouth opening or any jaw movement; and/or pain with jaw activities (yawning, kissing, talking); and/or pain with jaw habits (chewing gum, clenching, grinding).

At least a 50% reduction from baseline in monthly TMD days will be determined if the change in monthly TMD days from baseline phase through the 12 weeks treatment phase (3 cycles) * 100 / baseline monthly TMD days less than or equal to -50%.

Functional measures related to TMJ biomechanics and pain related behaviors:

TMD examination and Jaw functional limitation Scale: Change related to TMJ biomechanics/Jaw function and symptomatology in response to TMD examination.

Oral Behaviors (OBC): Changes in parafunctional behaviors

Pressure Pain Thresholds: Changes in myalgia and arthralgia

Graded Chronic Pain Scale (GCPS): Changes in pain intensity and pain related disability

Patient Global Impression of Change (PGIC): Assesses patient perspective of pain improvement

Hospital Anxiety and Depression Scale: Evaluation of Anxiety and depression

Exploratory Endpoint

To investigate the efficacy of Erenumab in decreasing pro-inflammatory cytokine release

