12 STATISTICAL CONSIDERATIONS

12.1 Study Hypotheses

The main objective of the statistical analysis is to estimate change in study endpoints and evaluate the efficacy of Erenumab by testing a priori hypothesis concerning the differences between treatment and placebo.

Erenumab reduces pain and restores function in patients suffering of TMD.

The primary efficacy hypothesis is that Erenumab produces greater change in average pain score (0-100 scale) from Visit 1 to Visit 4 than placebo.

The secondary efficacy hypothesis is that Erenumab produces a greater proportion of patients reaching at least a 50% reduction from baseline in monthly TMD pain days compared to placebo. This will be determined as a change from baseline phase (4 weeks) through the 12 weeks treatment phase (3 cycles) until Visit 4.

Functional measures related to TMJ biomechanics and pain related behaviors:

There is a greater proportion of patients achieving $\geq 30\%$ decrease (score) in limitation of jaw function with the use of erenumab after 12 weeks of treatment compared to placebo.

There is a greater proportion of patients achieving $\geq 30\%$ decrease (score) in oral behaviors with the use of erenumab after 12 weeks of treatment compared to placebo.

There is a greater proportion of patients achieving $\geq 30\%$ increase in value in pressure pain thresholds in temporalis, masseter, trapezius muscles, TMJs and epicondyles with the use of erenumab after 12 weeks of treatment compared to placebo.

There is a greater proportion of patients achieving $\geq 30\%$ decrease in intensity and pain related disability (GCPS) with the use of erenumab after 12 weeks of treatment compared to placebo.

There is a greater proportion of patients achieving $\geq 30\%$ increase in score (impression of improvement/ impression of change/PGIC) with the use of erenumab after 12 weeks of treatment compared to placebo.

There is a greater proportion of patients achieving $\geq 30\%$ decrease (score) in anxiety and depression (change in HADS) with the use of erenumab after 12 Weeks of treatment compared to placebo.

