12.4 Final Analysis Plan

The main goal of the statistical analyses is to estimate change in study primary and secondary endpoints to evaluate efficacy of Erenumab. Intention to treat analysis will be performed using a within-subjects student's pair t-test or repeated measures ANOVA (if more than two time points) to determine significant reduction in pain after drug intervention in each patient. Subsequently, a between-subjects unpaired t-test or two-way mixed designed ANOVA (if more than two time points) will be performed to determine difference between the placebo and erenumab groups. *Post-hoc analysis* will only be conducted following a significant ANOVA test, to protect from Type I errors. We will use a 2-way between subject's repeated measure ANOVA design to determine difference between the Erenumab group and placebo group, or a between-subjects unpaired t-test if two groups only. We will also use student's paired t-test to determine time points of significance. 50% reduction in pain days will be determined as a function of baseline pain days. Where, appropriate similar statistical procedures will be used for secondary endpoints.

Descriptive statistics for safety measures will also be calculated.

We will collect the following data for descriptive purposes and, if necessary, to use as covariates: Demographic information (age and race/ethnicity), rescue medication history, psychological factors and perceived change in overall status (PGIC).

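### At any anatomical site with a baseline pressure pain threshold above 3.846 kg, the 5 kg stimulation limit makes the 30% responder target unreachable, and the plan has no rule for this

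*Combined protocol and SAP*

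**What the plan says.** Section 8.1 (Pressure Pain Thresholds) defines the threshold as "the amount of pressure at which the participant first perceives pressure to be painful". Readings are repeated on each side and "the mean of the 2 closest values will be recorded as the threshold estimate". Then "The values from the right and left sides will be averaged to obtain a single PPT value per anatomical site". The stimulus is limited everywhere in the same way: "The cutoff pressure for all sites will be 5 kg". The section does not say what is entered when 5 kg is reached without pain.

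Section 12.1 makes PPT a responder endpoint. The hypothesis is that more participants on erenumab than on placebo reach, after 12 weeks, at least a 30% "increase in value in pressure pain thresholds in temporalis, masseter, trapezius muscles, TMJs and epicondyles". It gives no rule for turning five site results into one status per participant.

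Section 3.2.2 describes the same outcome without any threshold: "Pressure Pain Thresholds: Changes in myalgia and arthralgia". Section 12.4 adds only this: "Where, appropriate similar statistical procedures will be used for secondary endpoints". The procedures it refers to are t-tests and ANOVA. None of these sections mentions readings at the limit.

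**The concern.** A relative target combined with a fixed upper limit produces a ceiling. The higher a site's starting value, the less room there is to rise, and above a certain baseline the target lies outside the measurable range. For those sites the responder result is fixed before treatment starts.

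Two things follow for the comparison of arms. First, a fixed block of non-responses in both arms pulls the two proportions towards zero and narrows the gap between them. Second, about 30 participants per arm can differ by chance in how many high-threshold sites they have, which moves the responder proportions for reasons unrelated to the drug.

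No entry criterion in Sections 5.1 or 5.2 limits baseline PPT. Eligibility rests on a DC/TMD myalgia finding, for which Section 8.1 describes palpation of the masseter, temporalis and joint. Nothing requires the trapezius or lateral epicondyle to be tender, yet both share the same limit and the same 30% target.

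**Working it through.** **Inputs.** Limit 5 kg at every site, two closest readings averaged, then right and left averaged (Section 8.1). Responder target: a rise of at least 30% (Section 12.1). The plan states no baseline PPT and no power figure for this endpoint, so there is no figure of its own to reproduce. One assumption is needed: no pain at 5 kg is recorded as 5 kg.

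**Step 1: largest baseline that can respond.** The target from baseline b is 1.3 × b, and it must not exceed 5. So b ≤ 5/1.3 = 3.846 kg. The largest recordable rise is 5/b − 1.

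| Baseline (kg) | Target (kg) | Largest recordable rise | 30% reachable? |
|---|---|---|---|
| 3.00 | 3.900 | 66.7% | yes |
| 3.84 | 4.992 | 30.2% | yes |
| 3.85 | 5.005 | 29.9% | no |
| 4.00 | 5.200 | 25.0% | no |
| 4.50 | 5.850 | 11.1% | no |
| 5.00 | 6.500 | 0% | no |

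**Step 2: does averaging remove the limit?** No. Each side is capped at 5 kg, so the site mean is too. Sides of 2.7 and 5.0 kg give a mean of 3.85 kg and a largest rise of 29.9%. Averaging can also hide a capped reading. Sides of 5.0 kg (capped) and 2.0 kg give a mean of 3.5 kg, which is below 3.846 kg. The target is 1.3 × 3.5 = 4.55 kg. With one side held at 5.0 kg, the other must rise to 2 × 4.55 − 5.0 = 4.1 kg, about double its starting value.

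**Step 3: share of site values affected.** This depends wholly on assumed baselines. The table gives the area of a normal distribution above 3.846 kg, and the same area when the distribution is truncated at 5 kg.

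| Assumed mean/SD (kg) | Normal | Truncated at 5 kg |
|---|---|---|
| 1.5/0.6 | 0.005% | 0.005% |
| 2.0/0.7 | 0.4% | 0.4% |
| 2.5/0.8 | 4.6% | 4.5% |
| 3.0/1.0 | 19.9% | 18.0% |
| 3.5/1.0 | 36.5% | 31.9% |

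**Step 4: effect on a responder comparison at one site (illustration).** Let a share f of participants be unable to respond at that site, and let the rates among the rest be p1 and p2. The observed rates become (1 − f)p1 and (1 − f)p2. With assumed rates of 40% and 20% and f = 20%, these are 0.8 × 40% = 32% and 0.8 × 20% = 16%, so the difference falls from 20 to 16 percentage points. Section 12.2 assumes 15% dropout, which leaves 60 × 0.85 = 51 participants, or 26 v 25. By exact enumeration, the power of a two-sided 5% chi-square test falls from 35.4% to 27.2%.

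**Step 5: would dropping the high baselines repair the responder test?** With 20% removed from each arm, about 21 v 20 remain. At 40% v 20% the power is 27.4%, practically the same as the 27.2% without the restriction. The restriction removes the fixed failures but loses as much in numbers.

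**The case against.** The strongest reply is that this is a possible ceiling effect and not a contradiction, and that it may never matter. If baselines at the masticatory sites are low, as the myalgia criterion makes plausible, almost no site value lies above 3.846 kg: the first two rows of the Step 3 table give 0.4% or less. Section 3.2.2 already describes the outcome as a change, and Section 12.4 can be read as applying t-tests or ANOVA to it, so a continuous analysis may be intended anyway. The Manual of Procedures and a separate statistical analysis plan, both listed under Supplemental Materials and not part of this document, may say how cutoff readings are handled. Finally, the illustrated responder test has low power even without the cutoff.

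Most of this stands, and it limits the size of the point. It does not remove it: Section 12.1 states the responder hypothesis explicitly, and the document does not say how values at the limit enter it.

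A reader might also infer three stronger things that the documents do not support:

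- That any participant with a high baseline is a non-responder. The ceiling acts on each site value. Under an any-site rule, a high epicondyle value does not prevent a masseter response. Under an all-sites rule, a single high site is enough to fail.
- That the plan treats readings at 5 kg as exact. It is silent; its named methods have no provision for censoring, but that is not a stated rule.
- That chance baseline imbalance biases the comparison. Under randomization it adds variance; it does not shift the expected difference.

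**Conclusion.** The point holds for site values. Under the 5 kg limit, a site with a baseline above 3.846 kg cannot be recorded as a 30% responder, and averaging within or between sides does not change that. The arithmetic is certain, given that no pain at 5 kg is entered as 5 kg. The consequence is attenuation of a true difference in responder proportions, plus extra noise from chance imbalance.

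The size is unknown. Under the assumed distributions the affected share of site values runs from near 0% to about 36%, and the documents give no basis for choosing within that range. The effect on participant-level response cannot be worked out until the five sites have a combination rule. The matter concerns one secondary endpoint and leaves the primary endpoint untouched. It is of minor severity, but worth correcting because the correction is cheap.

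**What to change.** Leave the cutoff as it is and change the analysis wording:

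1. Make the main PPT analysis the continuous change to Visit 4 at each site, with baseline PPT as covariate. This agrees with the description in Section 3.2.2. Name the baseline visit, since Appendix A schedules PPT at both Visit 0 and Visit 1.
2. State what is recorded when 5 kg is reached without pain. Flag every such reading by side, before averaging, and treat it as right-censored, at least in a sensitivity analysis. Flagging only site means equal to 5 kg would miss the 5.0 and 2.0 kg case in Step 2.
3. Keep the 30% responder proportion as descriptive only, state how the five sites are combined, and report by arm and site how many baseline values exceeded 3.846 kg. Restricting the responder test to lower baselines is not a substitute, as Step 5 shows.

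The analysis uses measurements already planned; the one addition at the visit is to keep side-level readings with a flag for the limit. The cost is slightly more analysis work, and the responder proportion is no longer the main PPT test.

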8.2 Laboratory Procedures/Evaluations

8.2.1 Clinical Laboratory Evaluations

- Pregnancy test: Female participants of childbearing potential will be screened for pregnancy with a urine test (instant type) that will be performed at every study visit. The results will be read by the study staff. The urine will be discarded after the test.

8.2.2 Special Assays or Procedures

Blood Collection to evaluate cytokine profile

- A blood sample will be collected at Visits 0 and 4 by staff trained in phlebotomy. Blood samples will be evaluated then for the presence [REDACTED] cytokines by Luminex assay.
- Pre-collection preparation – participants do not require any special preparation for the sample collection.
- Mode of collection – A blood sample will be taken by a blood draw.
- Amount, frequency, and quality of specimen collection – The blood sample will consist of 10-15 ml this will be for each subject and will be taking on visits 1 and 4
- Specimen collection duration – We estimate that the collection procedure will have a duration of 15 minutes.

8.2.3 Specimen Preparation, Handling, and Storage

Collection of blood will be performed at the school of Dentistry and serum/plasma isolation and storage will be held at the same facility. The samples will be labeled with the same unique identification number provided for the participant at the moment of enrollment in our study and randomization. Peripheral blood leukocytes (PBLs) and plasma will be isolated from 10-15 ml of the subjects' blood and stored at -80°C. The plasma fraction will be used for analysis of the presence of soluble cytokines,

[REDACTED] by Luminex assay. At the end of the sample analysis, any remaining sample will be discarded.

8.2.4 Specimen Shipment

The analysis of the specimens will be performed by the Cytokine Core Laboratory (CCL).

9 ASSESSMENT OF SAFETY

9.1 Specification of Safety Parameters

This study involves the use of Erenumab, a fully human monoclonal antibody that is a CGRP receptor antagonist FDA approved for the prevention of migraine in adults

The participants of this study will be closely monitored and follow up in their clinic visits and between visits with telephone calls. As part of the study outcomes, the study staff will record information regarding AEs. Overall health parameters will be captured on case report forms. These will be completed at every visit and data will be compiled for review by the IRB.

The description of potential risks is described in 2.3 and 6.3. The most common side effects of the use of Erenumab are:

- Injection site reactions: which may include tenderness, pain, redness, itching, bruising, firmness, or hypersensitivity
- Constipation
- Muscle spasms/cramps
- Itching (pruritus)

Allergic reactions can happen within hours to days after using erenumab. Therefore, after the injection is administered, the participant will wait in the room for 20 minutes and the evening of the treatment visit, the participant will receive a follow up phone call and the information will be recorded.

If the participant reports a hypersensitivity reaction (rash, angioedema, anaphylaxis), new onset constipation or new onset of hypertension or any of the reactions described above, if there is worsening of TMD signs and symptoms during the 18 weeks of participation or if the participant decides against using Erenumab, he/she will be discontinued from the study (See 2.3.1 and 5.5.2).

The following expected events will not be considered reportable AEs:

- Temporary injection site reactions such as pain, erythema, pruritus after the injection of Erenumab
- Minor bleeding or bruising resulting from the blood draw
- Temporary pain or temporary increases in existing pain prompted during the TMD clinical examination or PPT.

9.1.1 *Unanticipated Problems*

The Office for Human Research Protections (OHRP) considers unanticipated problems involving risks to subjects or others to include, in general, any incident, experience, or outcome that meets **all** of the following criteria:

- Unexpected in terms of nature, severity, or frequency given (a) the research procedures that are described in the protocol-related documents, such as the IRB-approved research protocol and informed consent document; and (b) the characteristics of the subject population being studied;
- Related or possibly related to participation in the research (“possibly related” means there is a reasonable possibility that the incident, experience, or outcome may have been caused by the procedures involved in the research); and
- Suggests that the research places subjects or others at a greater risk of harm (including physical, psychological, economic, or social harm) than was previously known or recognized.

9.1.2 *Adverse Events*

An adverse event is any untoward or unfavorable medical occurrence in a human subject, including any abnormal sign (for example, abnormal physical exam or laboratory finding), symptom, or disease, temporally associated with the subject’s participation in the research, whether or not considered related to the subject’s participation in the research.

9.1.3 *Serious Adverse Events*

A serious adverse event (SAE) is one that meets one or more of the following criteria:

- Results in death
- Is life-threatening (places the subject at immediate risk of death from the event as it occurred)
- Results in inpatient hospitalization or prolongation of existing hospitalization
- Results in a persistent or significant disability or incapacity
- Results in a congenital anomaly or birth defect
- An important medical event that may not result in death, be life threatening, or require hospitalization may be considered an SAE when, based upon appropriate medical judgment, the event may jeopardize the subject and may require medical or surgical intervention to prevent one of the outcomes listed in this definition.

- Severe allergic reactions due to Erenumab: Severe skin reactions, difficulty breathing or swallowing.
- Severe constipation that may need hospitalization.

